5.2. Study Treatment Administration

Each dose of GB1211 and placebo will be administered orally with approximately 240 mL of room temperature water. In Part A, all doses will be administered after an overnight fast of at least 10 hours, with the exception of the food-effect cohort (planned to be Cohort A3), where the dose given in Treatment Period 2 will be administered 30 minutes after starting a high-fat breakfast. The dietary status for dosing in Parts B and C will be fasted unless data from the food-effect cohort is available and supports dosing in the fed state.

Subjects in Part A and B will be administered the IMP in numerical order while standing and will not be permitted to lie supine for 2 hours after dosing, except as necessitated by the occurrence of an AE(s) and/or study procedures.

In Part C, the doses of GB1211 (taken at the site) on Days 1/2 and Days 41/42 will be administered to subjects at the study site while standing and will not be permitted to lie supine for 2 hours after dosing, except as necessitated by occurrence of an AE(s) and/or study procedures; but all other doses will be administered by the subject at home.

5.3. Randomisation

For Parts A and B, the randomisation code will be produced by the statistics department at Covance using a computer-generated pseudo-random permutation procedure. Randomisation for Part C is to be confirmed.

In Part A, 2 subjects per cohort will be randomly assigned to receive placebo. For all cohorts in Part A (except the fed treatment period of the food-effect cohort), sentinel dosing will occur whereby 2 subjects (1 active and 1 placebo) will be dosed on 1 day and, providing no safety concerns arise, the remaining 6 subjects will be dosed after 24 hours.

Subjects in the food-effect cohort (planned to be Cohort A3) will be randomised to receive the same treatment in Treatment Periods 1 and 2.

In Part B, 3 subjects per cohort will be randomly assigned to receive placebo, and in Part C, 10 subjects in Cohort C1 will be randomly assigned to receive placebo.

Prior to the start of the study, live randomisation code will be distributed according to the randomisation specification form and will include the Covance CRU pharmacy staff.

5.4. Blinding

The following controls will be employed to maintain the double-blind status of the study:

- The placebo capsules will be identical in appearance to the GB1211.
- The Investigator and other members of staff involved with the study will remain blinded to the treatment randomisation code during the assembly procedure.
- Interim bioanalytical data will be provided to Covance in a blinded manner.
- Where possible, exploratory biomarker data will be provided to Covance in a blinded manner.

To maintain the blind, the Investigator will be provided with a sealed randomisation code for each subject, containing details of their treatment. These individual sealed envelopes will be kept in a limited access area that is accessible 24 hours a day. In order to manage subject safety or to support dose escalation decisions (in the event of possibly treatment-related SAEs or severe AEs), the decision to unblind resides solely with the Investigator. Whenever possible, and providing it does not interfere with or delay any decision in the best interest of the subject, the Investigator will discuss the intended code-break with the Sponsor. If it becomes necessary to break the code during the study, the date, time, and reason will be recorded in the subject's source data and on the individual envelope and will be witnessed by a second person.

5.5. Treatment Compliance

The following measures will be employed to ensure treatment compliance for Parts A and B:

- All doses will be administered under the supervision of suitably qualified study site staff.
- Immediately after dose administration, visual inspection of the mouth and hands will be performed for each subject.
- At each dosing occasion, a predose and postdose inventory of IMP will be performed on the dose containers.

For Part C, treatment compliance will be assessed based on the number of capsules provided on Day 1 compared to the number of capsules returned on Day 42.

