3.1.3. Part C (Optional)

Part C will comprise a multiple-dose cohort of 25 subjects with suspected NASH and liver fibrosis (Cohort C1). Part C may start following review of data from Part A and at least 1 Part B cohort.

Potential subjects will be screened to assess their eligibility to enter the study within 28 days prior to the first dose administration. Each subject will participate in 1 treatment period only and reside at the CRU from Day -1 (the day before dosing) until the morning of Day 2, returning for nonresidential visits on Days 7, 14, 21, 28, and 35. Subjects will then check back into the CRU on Day 41 until the morning of Day 43 (24 hours after the final dose on Day 42).

[figure not shown]
All subjects will return for a Follow-up visit 5 to 7 days after their final dose.

Dose Regimen:

For Part C, Cohort C1, 15 subjects will receive GB1211 and 10 subjects will receive placebo. The dietary state for dosing in Part C will be fasted unless data from the food-effect cohort is available and supports dosing in the fed state. For all subjects, the planned dosing will be BID on Days 1 to 41 inclusive, and a final single dose administration will occur in the morning of Day 42. The total daily dose administered, dose interval/frequency, and dosing duration will be based on review of data from Parts A and B.

An overview of the study design is shown in [Figure 6](#).

Figure 6: Study Schematic (Part C)

Abbreviations: BID = twice-daily; CRU = Clinical Research Unit

The dose level of Part C is to be determined following completion of Part A and at least 1 cohort of Part B.

The total duration of study participation for each subject (from Screening through Follow-up visit) for Cohort C1 is anticipated to be approximately 11 weeks.

A Schedule of Assessments is presented in [Appendix 6](#).

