7.1. Pharmacokinetic Assessments

7.1.1. Sample Collection and Processing

Blood samples (approximately 1 × 4 mL) will be collected by venipuncture or cannulation at the times indicated in the Schedule of Assessments in [Appendix 6](#). Furthermore, up to 3 additional blood samples may be taken from each subject per treatment period, with the maximum volume of blood withdrawn per subject not exceeding the limit detailed in [Appendix 3](#). Any changes to the scheduled times of PK assessments will be agreed with the Sponsor and documented in the TMF. Samples taken from subjects who received placebo will not be analysed.

Procedures for collection, processing, and shipping of PK blood samples will be detailed in a separate document.

Urine samples for Part A will be collected into preweighed polyethylene containers over the time intervals indicated in the Schedule of Assessments in [Appendix 6](#). Procedures for collection, processing, and shipping of PK urine samples will be detailed in a separate document.

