^b Timings relative to dose administration on Day 1.

^c In all females. Performed in serum at Screening and in urine at all other times. A positive urine pregnancy test will be confirmed with a serum pregnancy test.

^d Symptom-directed physical examination.

^e Body weight only.

^f In all females.

Table 3: Schedule of Assessments – Part C (Multiple Dose in Subjects with Suspected NASH and Liver Fibrosis)

Study Procedures	Screening	Day -1	Days 1 to 43	Follow-up (5-7 days Post-Final Dose)
Informed consent	X			
Inclusion/exclusion criteria	X	X		
Demographic data	X			
Medical history	X	X ^a		
Urinary drug screen	X	X		
Alcohol breath test	X	X		
Serology	X			
Pregnancy test ^c	X	X		X
Follicle-stimulating hormone	X ⁱ			
Height and body weight	X	X ^g		X ^g
Fibroscan CAP or Ultrasound ^e	X			
Site staff to query alcohol consumption prior to site visits ^f			At each site visit	X
Study residency:				
Check-in		X	Day 41	
Check-out			Day 2 and Day 43 (24 hours post-final dose)	
Nonresidential visit	X		Days 7, 14, 21, 28, and 35	X
Study drug administration:				
GB1211 or placebo			Days 1 to 41 (0 and 12 hour) and Day 42 (0 hour) ^b	
Pharmacokinetics:				
Blood sampling			Day 1: pre-am dose, 0.5, 1, 1.5, 2, 3, 4, 6, 8, and 12 hours post-am dose Day 2: pre-am dose (24 hours post Day 1 am dose) Day 42: predose, 0.5, 1, 1.5, 2, 3, 4, 6, 8, 12 hours post-final dose Day 43: 24 hours post-final dose	

Table 3: Schedule of Assessments – Part C (Multiple Dose in Subjects with Suspected NASH and Liver Fibrosis)

Study Procedures	Screening	Day -1	Days 1 to 43	Follow-up (5-7 days Post-Final Dose)
Exploratory biomarker assessments:				
Serum galectin-3			Day 1: pre-am dose Day 14, 28, and 42 ^h	
Fasting glucose and insulin			Day 1: pre-am dose Days 14, 28, and 42 ^h	
Lipid profile (eg, LDL, HDL, total cholesterol, and triglycerides)			Day 1: pre-am dose Days 14, 28, and 42 ^h	
hsCRP, IL-12, TNF- α , MCP-1, and proinflammatory chemokines (CCL2, CCL3, CCL4, and the chemokine receptors CCR1 and CCR2); and other biomarkers of inflammation as required			Day 1: pre-am dose Day 42 ^h	
Exploratory biomarkers of fibrosis (including but not limited to extracellular matrix proteins [TIMP-1, HA, and P3NP], A9, ELF panel, CK18, PAI-1, CH3L1, IL6, pro-collagen 3)			Day 1: pre-am dose Day 42 ^h	
Safety and tolerability:				
Adverse event recording	X	X	Ongoing	X
Prior/concomitant medication monitoring	X	X	Ongoing	X

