Table 3: Schedule of Assessments – Part C (Multiple Dose in Subjects with Suspected NASH and Liver Fibrosis)

Study Procedures	Screening	Day -1	Days 1 to 43	Follow-up (5-7 days Post-Final Dose)
Clinical laboratory evaluations (including HbA1c and coagulation profile)	X	X	Day 14 and Day 28: pre-am dose Day 43: 24 hours post-final dose	X
Vital sign measurements (blood pressure, pulse rate, and oral body temperature)	X		Day 1: pre-am dose, 4, and 8 hours post-am dose Day 2: pre-am dose Days 7, 14, 21, 28, and 35 Day 42: predose, 4, 8 hours post-final dose Day 43: 24 hours post-final dose	X
12-lead ECG	X		Day 1: pre-am dose and 4 hours post-am dose Days 14 and 28 Day 42: predose, 4 hours post-final dose Day 43: 24 hours post-final dose	X
Physical examination	X	X ^d	Day 1 ^d	X ^d

Abbreviations: CAP = Controlled Attenuation Parameter; CCL = chemokine (C-C motif) ligand; CCR = chemokine (C-C motif) ligand receptor; CH3L1 = chitinase-3 like protein-1; CK18 = cytokeratin 18; ECG = electrocardiogram; ELF = E74-like transcription factors; HA = hyaluronic acid; HbA1c = glycosylated haemoglobin; HDL = high density lipoprotein; hsCRP = heat shock C-reactive protein; IL = interleukin; LDL = low density lipoprotein; MCP1 = monocyte chemotactic protein-1; P3NP = aminoterminal peptide of pro-collagen III; PAI-1 = plasminogen activator inhibitor-1; NASH = nonalcoholic steatohepatitis; TIMP-1 = tissue inhibitor of matrix metalloproteinase-1; TNF- α = tumor necrosis factor-alpha.

^a Interim medical history.

^b Timings relative to dose administration on Day 1.

^c In all females. Performed in serum at Screening and in urine at all other times. A positive urine pregnancy test will be confirmed with a serum pregnancy test.

^d Symptom-directed physical examination.

^e Fibroscan only to be performed in subjects who do not have documented history of fatty liver.

^f Site to query whether subject has consumed alcohol within 36 hours of the site visit; and whether alcohol consumption has been limited to 2 units per day on all other days of study. Protocol deviations to be recorded if subject has not.

^g Body weight only.

^h Post dosing samples for biomarkers should be collected at approximately the same time each visit.

ⁱ In all females.

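### Part C checks adherence to about 77 home doses only once, by a capsule count after dosing ends, and Day 42 PK would probably not reveal missed doses

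*Protocol*

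**What the plan says.** Protocol section 3.1.3 plans Part C dosing as "BID on Days 1 to 41 inclusive, and a final single dose administration will occur in the morning of Day 42". Section 5.2 says that doses "taken at the site) on Days 1/2 and Days 41/42 will be administered to subjects at the study site", "but all other doses will be administered by the subject at home".

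For Part C, section 5.5 gives one adherence measure: "the number of capsules provided on Day 1 compared to the number of capsules returned on Day 42". In Parts A and B every dose is supervised, with mouth and hand checks and an inventory at each dosing occasion. Section 5.6 requires a record of what was dispensed and when, but no count during treatment.

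In Appendix 6, Table 3, the last early PK sample is "Day 2: pre-am dose (24 hours post Day 1 am dose"; the next is the Day 42 predose sample. Visits on Days 7, 14, 21, 28 and 35 fall between them. At each site visit staff ask about alcohol, but no capsule count, dosing record or PK sample is listed for those five visits. Clinical laboratory bloods are timed "Day 14 and Day 28: pre-am dose". Section 7.1.1 adds that "up to 3 additional blood samples may be taken from each subject per treatment period", without tying these to adherence.

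No adherence threshold or action is stated. The PK population (protocol section 8.2.2) has no adherence criterion, and SAP section 6.3 limits the SAP to Parts A and B.

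**The concern.** Part C has the longest dosing and is the only part dosed mainly at home, yet it has the weakest check on whether drug was taken. A single count on Day 42 comes too late to prompt any correction. It gives a total and no dates, so a subject who stopped for three weeks looks the same as one who missed scattered doses. It also treats a discarded capsule as a swallowed one.

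PK would be the natural cross-check, but the late profile follows doses given under supervision. Part B, which is fully supervised, has pre-dose samples on Days 4 to 9; Part C has no mid-course equivalent.

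Safety and tolerability of multiple doses in suspected NASH is a primary objective. Unrecognised under-dosing would make a benign safety record look as if it reflected 42 days of exposure, and would dilute biomarker changes. Serum galectin-3, glucose, insulin and lipids are also read on Days 14 and 28, when nothing measures exposure.

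**Working it through.** **1. Check of the PK schedule.** Appendix 6, Table 3 gives Day 1 (10) + Day 2 (1) + Day 42 (10) + Day 43 (1) = 22 samples. Appendix 3 states 22 for Part C. The figures agree, so no scheduled sample on Days 3 to 41 has been overlooked.

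**2. Home doses.** Planned doses: 41 × 2 + 1 = 83. Site doses: Day 1 morning and evening, Day 2 morning, Day 41 morning and evening, Day 42 morning = 6. Home doses: 83 − 6 = 77 (77/83 = 93%). No check-in time is given for Day 41; if that morning's dose is taken before arrival, home doses are 78 (94%). If the Day 14 and Day 28 morning doses were taken at the visit, the count is 75; if morning doses were taken on site at all five visits, it is 72 (87%).

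**3. What Day 42 PK would show if every home dose were missed.** Assumptions: linear one-compartment kinetics, a 12 h interval, steady state under full adherence. Let r = 2^(−12/t½).

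- Doses given k or more intervals before the Day 42 dose supply r^k of the adherent Day 42 AUC0-tau.
- Both Day 41 doses supervised: home doses start three intervals back, so the retained AUC is 1 − r³.
- Only the Day 41 evening dose supervised: retained AUC is 1 − r².
- Home-dose share of the Day 42 predose level: r² and r respectively.

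Half-lives of 4.47 and 8.23 h are the dog range in protocol section 1.5. No human value is given; 12 h and 24 h are assumptions.

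| t½ (h) | r | AUC retained, both Day 41 doses supervised | AUC retained, evening only | Predose share from home doses, both | Predose share, evening only |
|---|---|---|---|---|---|
| 4.47 | 0.156 | 99.6% | 97.6% | 2.4% | 15.6% |
| 8.23 | 0.364 | 95.2% | 86.8% | 13.3% | 36.4% |
| 12 | 0.500 | 87.5% | 75.0% | 25.0% | 50.0% |
| 24 | 0.707 | 64.6% | 50.0% | 50.0% | 70.7% |

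At the mouse half-lives (1.93 to 3.63 h, same section), retained AUC is 99.9% or more with both Day 41 doses supervised.

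**4. What a mid-course predose sample could add.** The previous day's two doses supply 1 − r² of a trough: 97.6% at 4.47 h and 86.8% at 8.23 h. Such a sample would show recent dosing, not the whole interval since the last visit.

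**5. Cost of two extra samples.** Blood: 214.3 + 2 × 4 = 222.3 mL. Placebo samples are not analysed (section 7.1.1), so assays are at most 15 × 2 = 30.

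**The case against.** A reader might infer that non-adherence would go unseen altogether. The documents do not support that: a subject who skips doses and returns the capsules is identified on Day 42. What escapes is discarded capsules, timing, and any chance to correct.

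A reader might also infer that the count mixes supervised with home doses. The protocol does not say whether site doses come from the subject's issued supply. If they do, the distortion is small: 50% home adherence would read as (38.5 + 6)/83 = 54%. Nor is it right that Part C has no troughs; Day 2 and Day 42 both have pre-dose samples, and only the mid-course is empty.

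The PK argument is conditional, and this is the strongest objection. Protocol section 1.5 reports extensive turnover in dog and mouse hepatocytes and negligible turnover in human ones, so human half-life may be longer than in animals. Mouse exposure also fell by Day 42 (50 mg/kg males, AUC 85188.1 to 41631.3 ng.h/mL), so simple superposition is not secure. The Day 42 predose level is more sensitive than AUC. Against this, section 3.4.1 expects no accumulation, which points to a short half-life, though that too rests on nonclinical data. The objection stands as a limit: Day 42 PK would probably not reveal missed home doses, but this cannot be asserted outright.

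Finally, Part C is optional, its interval and duration may change, and its analyses are unpowered and descriptive. That limits the weight of the point but does not remove it.

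**Conclusion.** The point holds as a low-cost improvement. On the planned BID schedule, 77 or 78 of 83 doses are unsupervised and adherence is assessed once, after dosing has ended. That much rests on the documents alone.

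The further statement that Day 42 PK would probably not expose missed home doses depends on linear kinetics and a half-life near the dog range; at about 24 h it would fail. Human half-life from Parts A and B should be available before Part C starts and would settle this. The capsule count remains late and undated whatever the half-life.

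The effect is on interpretation: safety exposure could be overstated and biomarker changes diluted. No formal test or error rate is affected.

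The Day 14 and Day 28 timing is a separate matter. Home dosing in section 5.2 and pre-dose bloods in Appendix 6 may be compatible if the subject doses after the visit, but the text does not say so. A reader might infer a flat contradiction; the documents show only an ambiguity.

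**What to change.** - **Section 5.5:** count returned capsules on Days 7, 14, 21, 28 and 35 and at Day 41 check-in, re-instruct at the visit where needed, and report home-dose adherence separately from site doses.
- **Appendix 6, Table 3 (optional):** schedule one 4 mL predose PK sample on Days 14 and 28 alongside bloods already drawn, described as a spot check of recent dosing only. Section 7.1.1 already allows up to three extra samples and lets PK times change by agreement with the sponsor.
- **Section 5.2 and Appendix 6, Table 3:** reconcile the home-dosing statement with the pre-dose bloods on Days 14 and 28. The sponsor must settle which reading applies.

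Cost: amendment wording and a few minutes per visit for the counts. The optional samples add 8 mL of blood per subject (214.3 to 222.3 mL) and at most 30 assays for the 15 active subjects.

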5.6. Drug Accountability

The Investigator (or designee) will maintain an accurate record of the receipt of the study supplies received. In addition, an accurate drug disposition record will be kept, specifying the amount dispensed to each subject and the date of dispensing. This drug accountability record will be available for inspection at any time. At the completion of the study, the original drug accountability record will be available for review by the Sponsor upon request.

For each batch of unit doses, the empty used unit dose containers will be discarded upon satisfactory completion of the compliance and accountability procedures. Any unused assembled unit doses will be retained until completion of the study.

At the completion of the study, all unused supplies will be returned to the Sponsor or disposed of by the study site, per the Sponsor's written instructions.

6. CONCOMITANT THERAPIES AND OTHER RESTRICTIONS

6.1. Concomitant Therapies

6.1.1. Concomitant Therapies for Parts A and B

Subjects of Part A and B will refrain from use of any prescription or nonprescription medications/products during the study until the Follow-up visit, unless the Investigator (or designee) and/or Sponsor have given their prior consent.

Paracetamol/acetaminophen (2 g/day for up to 3 consecutive days), hormone replacement therapy, oral, implantable, transdermal, injectable, or intrauterine contraceptives are acceptable concomitant medications.

The administration of any other concomitant medications during the study is prohibited without prior approval of the Investigator (or designee), unless its use is deemed necessary for treatment of an AE. Any medication taken by a subject during the course of the study and the reason for its use will be documented in the source data.

6.1.2. Concomitant Therapies for Part C

Subjects of Part C will refrain from use of any prescription or nonprescription medications/products during the study with exceptions, as stated in [Section 4.6](#), until the Follow-up visit, unless the Investigator (or designee) and/or Sponsor have given their prior consent.

Paracetamol/acetaminophen (2 g/day for up to 3 consecutive days) and hormone replacement therapy are acceptable concomitant medications.

The administration of any other concomitant medications during the study is prohibited without prior approval of the Investigator (or designee), unless its use is deemed necessary for treatment of an AE. Any medication taken by a subject during the course of the study and the reason for its use will be documented in the source data.

6.2. Diet

6.2.1. Parts A and B

While confined at the study site for Parts A and B, subjects will receive a standardised diet at scheduled times that do not conflict with other study-related activities. Subjects will be fasted overnight (at least 8 hours) before collection of blood samples for clinical laboratory evaluations.

On the days with intensive PK assessments (Day 1 for Part A and Days 1 and 10 for Part B), meals will be identical for each cohort, with the exception of the high-fat breakfast for the food-effect cohort (planned to be Cohort A3).

On Day 1 in Part A, subjects will be fasted for at least 10 hours prior to study drug administration until 4 hours postdose, when a meal will be provided (lunch times on Day 1 will be staggered between subjects to ensure this). With the exception of water given with the dose, subjects will not be allowed fluids from 1 hour prior to until 2 hours after dosing. Meals will be provided as appropriate at other times. Other than the fluid restrictions on dosing days, water will be freely available at all times.

For the food-effect cohort (planned to be Cohort A3), subjects receiving the GB1211 or placebo under fed conditions will consume the following high-fat breakfast (Table 5) before dosing. Subjects should start the meal 30 minutes prior to administration of the IMP. Study subjects should eat this meal in 30 minutes or less. The drug product should be administered 30 minutes after start of the meal.

Table 5: High-fat Breakfast Content

High-fat Breakfast
120 g fried eggs (2 eggs) in vegetable oil
50 g bacon (2 rashers)
72 g toasted white bread (2 slices)
13 g butter (2 pats)
108 g hash brown (3 each)
240 g whole milk
Total calories: 973 kcal

This high-fat meal contains the equivalent of approximately 150 protein calories, 250 carbohydrate calories, and 500 to 600 fat calories.

In Part B, the time interval between meals and dosing will be determined by the PK data from Part A and will be documented in the TMF. Meals will be provided as appropriate at other times. With the exception of water given with the dose, subjects will not be allowed fluids from 1 hour prior to dosing until 2 hours after dosing. Other than these fluid restrictions, water will be freely available at all times.

For Parts A and B, foods and beverages containing poppy seeds, grapefruit, or Seville oranges will not be allowed from 7 days prior to Check-in until the Follow-up visit. Caffeine-containing foods and beverages will not be allowed from 36 hours before Check-in until Discharge.

Consumption of alcohol will not be permitted from 36 hours prior to Check-in until the Follow-up visit.

